### **5.2.3 Subgroup Analyses**

Subgroups will be defined based on randomization stratification and background or baseline characteristics.

The following subgroup analyses are planned:

- ApoE status: subjects will be classified according they have 1 or 2 copies of E4 (one group) or zero copy of E4 (one group). Efficacy analyses will be done for these subgroups.
  - E4=yes
  - E4=no
- Randomization stratification is done on the presenting ADAS-cog value (which is the screening assessment, due to the intention for the score to be evaluated for validity based on external review of the scoring). Subgroups will be defined by the randomization stratum of ADAS-cog 19 or less (one group) or ADAS-cog more than 19 (one group). Efficacy analysis will be done for these subgroups:
  - ADAS-cog 19 or less
  - ADAS-cog more than 19
- Years since diagnosis is calculated based on the date of diagnosis of AD. Subjects with date of diagnosis within 3 months or those with date of diagnosis more than 5 years have questionable status for having declining mild AD on stable medication for AD for at least 3 months. Efficacy analysis will be done for these subgroups:
  - Years since diagnosis between 3 months and 3 years
  - Years since diagnosis between 3 years and 5 years
  - Years since diagnosis more than 5 years.

### **5.2.4 MRI and PET Variables**

For imaging variables, MRI variables are specified; PET variables are considered to be exploratory and will be specified separately. Statistical methodology will include stratification for A-study and B-study, acknowledging that the analysis of imaging data is intended to be for

the combined studies. Methodology for MRI will be similar to that for other secondary variables of analysis. Statistical methodology for PET variables will be described in the CSR.

Statistical methodology will include main-effects ANCOVA on change from baseline (adjusted for skull size). Supportive analysis will include Rank ANCOVA.

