4.0 SUBJECT SELECTION

4.1 INCLUSION CRITERIA

Subject eligibility should be reviewed and documented by an appropriately qualified member of the Principal Investigator's (PI's) study team before participants are included in the study.

1. Evidence of a personally signed and dated informed consent document indicating that the subject (or a legally authorized representative) and caregiver/informant has been informed of all pertinent aspects of the study. Participants must be able to provide assent (where this is in accordance with local laws, regulations and ethics committee policy) and assent may be re-evaluated during the study at regular intervals.
2. Participants and caregiver/informants who are willing and able to comply with scheduled visits, treatment plan, laboratory tests, and other study procedures.
3. The subject must have a reliable caregiver/informant with regular contact (i.e., 10 hours a week as combination of face-to-face visits and telephone contact acceptable) who will facilitate the subject's full participation in the study. Caregivers/informant must have sufficient subject interaction to be able to provide meaningful input into the rating scales administered in this study where caregiver/informant input is required, in particular the CDR and evidence of this should be documented in source documentation. Participants who reside in assisted living facilities are permitted provided that they meet caregiver/informant criteria.
4. Participants and caregiver/informants must be able to read, write, and speak the language in which psychometric tests are provided with visual and auditory acuity (corrected) sufficient to allow for accurate psychometric testing.
5. Males and females (of non-childbearing potential) ages ≥ 50 years of age at screening.

6. Diagnosis of probable AD, consistent with the criteria from the 2011 National Institute on Aging and the Alzheimer's Association workgroup (McKhann et al., 2011). Evidence of progression needs to be documented in source documentation at the time of screening based on review of prior medical records and/or information gathered from the subject or caregiver/informant(s). Biomarker evidence of the pathophysiological process or neuronal injury associated with AD should be documented if data is available in participant's medical records (not specifically measured for inclusion in this study).

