### 5.2 Statistical Methodology for Efficacy Analysis

Efficacy evaluations will include the co-primary endpoints (ADAS-cog and CDR-sb), key secondary endpoint, secondary endpoints and other efficacy variables.

The primary analysis of efficacy endpoints will be done on the FAS with supportive and sensitivity analyses done to examine robustness against analysis assumptions and handling of missing data.

Statistical analysis will be done on the A-study and the B-study, independently, for the co-primary variables: change from baseline in ADAS-cog and change from baseline in CDR-sb. The A-study includes the first approximately 400 patients randomized, and the B-study includes the remaining approximately 400 patients randomized. For all other secondary variables and subgroup analyses, the study as a whole (A-study and B-study combined) will be used for inferential purposes. It is noted that randomization supports independent analysis of A-study and B-study.

The primary analysis will be done for the A-study and the B-study separately, and each will use  $\alpha = 0.049$ , which includes an adjustment of 0.001 for interim analyses performed by the Independent Data Monitoring Committee (IDMC), thereby preserving the overall study-wise  $\alpha = 0.05$ .

This study is randomized using site randomization; the study randomization also includes a randomization stratum for severity of AD using a cut-point of 19 on the ADAS-cog at the time of randomization (screening values are used, due to the expectation that a confirming evaluation would be done). Efficacy analyses will be done including randomization stratum as a main effect.

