- First, for patients with intermittent missing values, before performing the MI, a monotone missingness pattern will be created. Intermittent missing values will be imputed using the Markov Chain Monte Carlo (MCMC) methodology which assumes a multivariate normal distribution over all variables included in the imputation model. The imputation model will be performed by treatment group and will include age, sex, ApoE status, education level, body weight (or BMI), baseline stratum, baseline and observed values at Months 3, 6, 9, 12, 15 and 18. Months 9 and 12 are not included in the model for endpoints which were not scheduled to be assessed at those visits. The MI procedure in SAS will be used for this purpose and this first MI step is planned to be repeated 100 times, creating several different datasets with a monotone missing data structure. A unique seed value will be used in the MI procedure and documented to allow for replication. The imputation is based on the missing at random (MAR) assumption, i.e. the missing data are assumed to follow the same model as the other patients in their respective treatment arm.
- After this, the remaining missing data will be imputed using a method for monotone missingness, also based on the MAR assumption. Thus, for each of the 100 created datasets with a monotone missing data pattern, the MI procedure in SAS will be used to impute missing values based on a sequential procedure reflecting the monotone missing data pattern. A seed value of 446786 will be used for this second invocation of the MI procedure. Patients with the first missing value occurring at Month 3 will have their missing Month 3 value replaced by an imputed value from a regression model by treatment group with age, sex, ApoE status, education level, BMI, baseline stratum, and baseline as potentially predictive variables.
- In the next step, patients with the first missing value occurring at Month 6 will have their missing Month 6 value replaced by an imputed value from a regression model with Month 3 data, in addition to the variables listed above.
- The same procedure will be repeated for all other visits.

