- The imputed datasets generated with the approach described above do contain only non-missing values and are used as input in the model for the supportive analysis of the primary endpoint. MMRM models similar to what are described above will thus be run on each of the generated imputed datasets and the difference between the treatment groups at Month 18 will be estimated. The MMRM model will be similar to the primary analysis. Finally, the MIANALYZE procedure in SAS will be applied to combine the results from these several datasets to derive an overall estimate of the treatment difference at Month 18. In addition to the estimates, corresponding 95% confidence intervals and p-values will be calculated.

Another MI analysis will be performed with the assumption that the data in the active treatment group are missing not at random (MNAR). A tipping point-based assumption will be used, i.e. the trajectories of the patients in the active treatment group after withdrawal are assumed to be worse by an amount of delta. After the MI using the MAR assumption, as defined above has been done, the amount of delta will be added to each imputed value in the active treatment group. Successively harsher deltas will be imposed on the imputed values in the active group, starting with an ADAS-cog increment (worsening) of 0.25 points or a CDR-sb increment

(worsening) of 0.1 points. The delta is further increased in the steps of 0.25 points (e.g., 0.50, 0.75) for ADAS-cog or in the steps of 0.1 points (e.g., 0.2, 0.3) for CDR-sb until the statistical significance is lost, i.e., until the p-value becomes more than 0.049. For the placebo group, the MI using MAR assumption will be used.

Further MI analysis assuming MNAR will be done using the Copy Reference approach. Placebo-group based assumption will be used, i.e. the trajectories of the patients are assumed to follow the placebo group after the discontinuation. Methods similar to those described above will be used to generate monotone missing data. After this, the missing data will be imputed sequentially for each visit (e.g., Month 3, Month 6). Only the data from the placebo group will be used for the imputation.

For the ANCOVA models, data from baseline and Month 18 will be used. Analysis will include treatment, baseline stratum as fixed factors and Baseline as covariate. For the LOCF analysis, the last available measurement will be used to impute the Month 18 data in case of missing data.

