## 5.2.2 Statistical Methods for Secondary Variables

Secondary and exploratory endpoints that are measurement variables will use similar statistical methodology to the methodology used for primary analysis. Stratification for A-study and B-study will be done as for primary variables. Efficacy variables that are proportions will be analyzed using Mantel-Haenszel test, controlling for Stratum, if appropriate. For the analysis of the categories for responders, a Cochran-Mantel-Haenszel test will be used. Methodologies for variables that are proportions will include construction of confidence intervals for each group and for the difference between groups. For analysis, Fisher's exact test will be used for single-population analysis, and a Mantel-Haenszel test will be used for analyses combining data across strata.

Responders based on the ADAS-cog total score, will be assessed using cumulative percentage plots. Similarly, responders based on the CDR-sb score will be assessed using cumulative percentage plots. The y-axis will show the cumulative percentage of patients who achieved the specific measure of improvement in the ADAS-cog (or CDR-sb) total score shown on the x-axis with a separate cumulative percentage curve for each treatment group.

The proportion of participants who experience loss of one global stage on the CDR will be assessed at each Visit using logistic regression with treatment (as a categorical/class variable), and baseline CDR global score (as a continuous variable). Summary measures from the analysis will include the odds ratio, 95% confidence interval for the odds ratio, and p-value for treatment comparison. Additionally, the proportion of participants in each CDR global stage will be presented.

Kaplan-Meier plots will be provided for each time-to-event variable. For each day, the "survival probability" will be computed by the product-limit method. Time-to-event endpoints may be modelled using Cox proportional hazards models with fixed effects for treatment and baseline measures as a covariate for supportive purposes. The estimated hazard ratio between Azeliragon and placebo will be presented with associated p-values and 95% confidence intervals.

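### The Stage 2 hippocampal-volume ANCOVA leaves out age, sex and ApoE4 status, which the trial already collects, so some precision may be lost

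*SAP*

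**What the plan says.** The key secondary endpoint is Month 18 change in hippocampal volume (SAP 4.1.2), tested in both sub-studies combined (SAP 2, Stage 2). The model has to be assembled from several places:

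- SAP 5.2.4 gives the model type and one adjustment: "Statistical methodology will include main-effects ANCOVA on change from baseline (adjusted for skull size".
- The same section adds the sub-study: "Statistical methodology will include stratification for A-study and B-study".
- It then refers onward: "Methodology for MRI will be similar to that for other secondary variables of analysis".
- SAP 5.2.2 refers onward again: "Secondary and exploratory endpoints that are measurement variables will use similar statistical methodology to the methodology used for primary analysis".
- For ANCOVA, SAP 5.2.1 says: "Analysis will include treatment, baseline stratum as fixed factors and Baseline as covariate". SAP 5.2 agrees on the stratum: "Efficacy analyses will be done including randomization stratum as a main effect".

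Read together, the model holds treatment, sub-study, ADAS-cog stratum, baseline volume and skull size.

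Age, sex and ApoE status are covariates in no efficacy model in the SAP. They do appear in the multiple-imputation regressions of SAP 5.2.1, which list "age, sex, ApoE status, education level, BMI, baseline stratum, and baseline as potentially predictive variables". ApoE4 carriage is also a planned subgroup factor (SAP 5.2.3). Date of birth and sex are recorded at screening (Protocol 6.1), and blood for ApoE genotyping is drawn at baseline (Protocol 6.2.1 and 7.9). Entry is open to "ages ≥ 50 years of age at screening", with no upper limit.

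**The concern.** In a linear model for a randomized comparison, a pre-treatment covariate that predicts the outcome removes variance from the residual and narrows the confidence interval for the treatment effect. Here three candidate predictors are already planned for collection, and the SAP itself regards them as worth using when it imputes other outcomes.

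This endpoint has few other routes to precision. Volumes are computed only at screening and Month 18 (Protocol 7.6), so no intermediate visits contribute as they do in the co-primary MMRM. Patients who qualified by CT do not contribute at all (Protocol 7.7). The documents contain no power calculation for the endpoint.

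At stake is the chance of success on the test that serves the disease-modification aim. It must also be significant before any of the eight ranked secondary endpoints in SAP 4.1.3 can be tested (SAP 2, Stage 3).

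**Working it through.** **Figures in the plan.** There is no standard deviation, effect size, power or R² for hippocampal volume, so there is no MRI figure to reproduce. The nearest are the co-primary sample sizes (Protocol 9.1), which do reproduce:

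- ADAS-cog, difference 3.5, SD 9: an exact t-test with 141 per group has 90.2% power. 141/0.8 rounds up to 177 per arm, or 354.
- CDR-sb, difference 0.9, SD 2.4: 152 per group has 90.3% power. 152/0.8 = 190 per arm, or 380.

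They say nothing about the MRI model beyond supplying the 20% dropout used next.

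**Assumptions.**

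- 800 randomized with 20% loss gives 640 scans, 320 per arm. CT-qualified patients would lower this, but the ratios below do not depend on it.
- Two-sided 0.05. The effect is set so that power without the added covariates is 80%: (1.960 + 0.842) × √(2/320) = 0.221 SD.
- R² is the share of residual variance that age, sex and ApoE4 explain beyond sub-study, stratum, baseline volume and skull size. It is unknown and is shown as a range.

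**Formulas.** The standard error is multiplied by √(1 − R²). The equivalent gain in patients is 1/(1 − R²) − 1. Power is Φ[(1.960 + 0.842)/√(1 − R²) − 1.960].

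| Assumed R² | SE factor | SE reduction | Equivalent extra patients | Power from 80% |
|---|---|---|---|---|
| 0.01 | 0.995 | 0.5% | 1.0% | 80.4% |
| 0.02 | 0.990 | 1.0% | 2.0% | 80.8% |
| 0.05 | 0.975 | 2.5% | 5.3% | 82.0% |
| 0.10 | 0.949 | 5.1% | 11.1% | 84.0% |

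The table is before the cost of the extra parameters.

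**Cost of the extra parameters.** The present model has five terms and an intercept, leaving 640 − 6 = 634 residual degrees of freedom. Three more leave 631. The variance cost is about 634/631 = 1.0048, or 0.5%. Solving (1 − R²) × 1.0048 = 1 gives R² of about 0.005 as the break-even point. A fourth parameter, for missing ApoE, gives 634/630 = 1.0063 and a break-even of about 0.006.

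**Cost of a missing genotype.** ANCOVA drops patients with a missing covariate unless a rule says otherwise. If 2% of scanned patients lacked an ApoE result, the gain at R² = 0.02 would vanish: 1.02 × 0.98 is about 1.00. The documents do not say how many results will be missing.

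**The case against.** The strongest case against is that the loss is not shown from the documents.

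A reader might infer that the SAP itself concedes that age, sex and ApoE status predict hippocampal change. It does not. The imputation models serve ADAS-cog and CDR-sb, where such variables help to make missing-at-random plausible. The list also contains education and BMI, which are not proposed here. The ApoE4 subgroup asks whether the treatment effect differs, not whether ApoE4 is prognostic. Moreover, baseline volume, skull size and ADAS-cog stratum may already carry part of any age or sex signal, so the added R² could be small. All of this stands, and it is why the loss is put as possible and its size as an assumption.

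A reader might also take the ANCOVA sentence to mean that skull size is the only adjustment. The rest of SAP 5.2.4 and its cross-references rule that out.

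It can further be said that baseline plus stratum is the SAP's consistent pattern, a defensible prespecified choice, and that Stage 2 is reached only if all four Stage 1 tests succeed. Both are true. They limit the importance of the point. They do not remove a small improvement that is available on data already collected.

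**Conclusion.** The point holds as an optional improvement. The Stage 2 model omits three pre-treatment covariates that are already collected, and precision may be lost as a result. For an assumed added R² of 2% to 10%, the standard error would fall by 1% to 5% and power would rise by roughly 1 to 4 points from 80%, before a variance cost of about 0.5%. Below an R² of about 0.005 there is no net gain.

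Two stronger readings should be set aside. The omission does not bias the treatment comparison or raise the type I error, because treatment is randomized: this is a matter of efficiency only. Nor is the gain free, since it uses three or four degrees of freedom and could be undone by missing genotypes without a rule for them.

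A related gap makes the edit more worthwhile. Protocol 9.2 leaves the MRI methodology to be detailed in the SAP, yet the SAP never lists the covariates in one place, and it does not say whether skull size is a covariate or is used to normalize the volumes.

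**What to change.** Before unblinding, by tracked amendment, state in SAP 5.2.4:

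> The key secondary analysis is an ANCOVA on change in hippocampal volume to Month 18, with terms for treatment, sub-study (A or B), ADAS-cog randomization stratum, baseline hippocampal volume, skull size (entered as a covariate), age, sex and ApoE4 status (carrier, non-carrier, result missing).

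Use the same covariates for ventricular and whole-brain volume, each with its own baseline volume.

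The cost is a short SAP edit and no new data. The model uses three more degrees of freedom, or four if any ApoE result is missing, which is about 0.5% to 0.6% of variance at roughly 640 scans. The terms should be fixed while the data are still blinded, because covariates added later would look data-driven.

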### **5.3 Disposition, Demography, and Baseline Characteristics**

A tabulation of subject disposition will be presented, including the number screened, the number randomized in each population group, the number dosed in each population group, the number who withdrew prior to completing the study, and reasons for withdrawal.

Demographic and baseline characteristics (disease history, medical history, and prior treatments for AD) will be summarized for all randomized patients and for the FAS. No formal statistical comparisons will be performed. Summaries of continuous variables will include number of patients, mean, median, minimum, maximum, and standard deviation. Summaries of categorical variables will include numbers of patients in each category.

The variables to be summarized will include:

- Age, gender, race, and ethnicity
- Weight, height, BMI
- Years since diagnosis of AD
- Baseline MMSE
- ApoE status
- Education level
- Background AD medications (ACHEI, Memantine, Both).

### **5.4 Analysis of Safety Data**

#### **5.4.1 Adverse Events**

Adverse events reported in this study will be coded using MedDRA®, Version 16.0, or later. Coding will be to the lowest level terms (LLT). The verbatim text, the preferred term, and the primary system organ class (SOC) will be listed in subject listings. Summaries that include frequencies and proportions of patients reporting AEs will include the preferred terms and the SOCs. Summaries will include TEAEs by severity and by relationship to study medication.

Adverse event summaries will be constructed displaying AEs in decreasing order of total frequency according to the numbers of subjects reporting the AE (not the number of reports).

- Number (percent) of subjects reporting TEAE by treatment and overall in accordance with variables listed in [Section 4.1.1](#).

Supportive listings will be constructed that includes the subject identification, the treatment group, TEAEs, MedDRA terms, seriousness, severity, causality, elapsed time to onset, duration, and outcome.

Methodology for AESIs will follow the same methodology for TEAEs.

